The benefits of AVF over AVG are least certain in older adults, as age-related biological changes independently modulate patient outcomes.¹⁰ Nationally representative cohort studies of older adults with incident ESKD have shown similar patient survival between those whose first AV access placed or used was a fistula or a graft.^{11,12} Compared with grafts, fistulas fail more often and necessitate longer times and more subsequent procedures to aid development, exposing older patients to time-consuming procedures that may negatively affect upper extremity strength and erode their quality of life.¹³⁻¹⁶ Hitherto, the contribution of pre-operative muscle strength to AV access outcomes and the impact of AV access placement on upper extremity strength and self-sufficiency have not been evaluated. We propose a randomized pilot trial in older adults with pre-dialysis advanced chronic kidney disease (CKD) or incident ESKD using a TCVC for HD who had no prior AV access surgery and have upper extremity vasculature suitable for either fistula or graft placement. Participants will be randomized to receive an upper extremity AVF-first or AVG-first access for HD.

Objectives

The primary objective of this study is to prospectively evaluate patient and vascular access outcomes in a randomized intervention and in a patient population in whom fistula-first guidelines have been applied despite the lack of proven benefit and at the detriment of more access failures and procedures. Our hypothesis is that there is a bidirectional relationship between the type of first AV access and patient outcomes as follows: a) the graft-first strategy will confer a more effective transition from TCVC-based to AV access-based HD and will limit upper extremity functional impairment from protracted access development and subsequent access procedures, and b) preoperative muscle strength will impact AVF development.

Methods and Measures

Design

This randomized pilot trial will be parallel-arm in design (Appendix A). We plan to enroll 50 patients of age ≥ 65 years, with incident ESKD or advanced CKD expected to require HD initiation within 90 days of screening. Screening for potential participants will be performed

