We will begin by examining descriptive statistics (means, standard deviations, minima, quartiles, maxima) and plots of the data (histograms and boxplots) to become familiar with the data and check for outliers. The proportion of people meeting each of the feasibility and protocol adherence endpoints with accompanying 95% confidence intervals (CI) will be calculated using skew-corrected score tests with a continuity correction. The maximum uncorrected error margin associated with the estimation of consent and surgery rates is 0.138, obtained at $p=0.5$. This suggests that CI around these estimates will be tight enough to provide meaningful guideline in the design of the larger trial. We will describe participant characteristics and evaluate reasons for protocol violations. We will calculate rates of dropout and other events, although we expect low numbers. Robust regression and non-parametric methods will be used for comparisons between randomized arms. The associations between pre-operative muscle strength (continuous or binary variable) with AV access primary outcome will be tested using logistic regression. The participants will be followed for a minimum of 12 months following index AV access placement. Participants who undergo AV access placement >90 days after randomization or who experience primary or secondary AV access failure will be analyzed as randomized in the intention-to-treat (ITT) analysis. Missing data will be handled under the missing at random (MAR) assumptions in compliance with an ITT protocol.²⁶ We will pay close attention to variables with higher rates of missingness, relative to others or display missingness patterns that deviate from the MAR assumptions since they could inform and guide the development of the larger trial. Results from the pilot analyses are likely to have high variability, but will provide valuable insight that will be considered in the design of a larger trial.

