Appendix D. Vascular access outcomes

Vascular access outcomes (according to the recommendations of the Committee on Reporting Standards for Arteriovenous Accesses, Society for Vascular Surgery and American Association for Vascular Surgery)	
AV access outcome	Definition
Primary access failure	Permanent failure of the fistula or graft before hemodialysis suitability. This includes inadequate maturation, thrombosis, failure of first and subsequent cannulations, and other complications leading to nonfunctional fistula or graft.
Successful cannulation	The arteriovenous access became the primary vascular access for hemodialysis (the fistula or graft access has been cannulated with two 16- or 15-gauge needles for ≥ 3 consecutive dialysis sessions and the TCVC was removed).
Suitability for hemodialysis	Fistula or graft use with two needles and maintenance of blood flow $\geq 300\text{ml}/\text{min}$ for $\geq 75\%$ of dialysis sessions over a continuous 4-week. The maturation criteria can be satisfied at any time within 6 months of fistula or graft creation surgery.
Unassisted access maturation	Criteria for fistula or graft suitable for hemodialysis (based on the above criteria) are met before any endovascular or secondary surgical procedure to facilitate maturation.
Assisted access maturation	Satisfaction of the criteria for fistula or graft suitability for hemodialysis after a procedure to facilitate maturation (e.g., angioplasty, stent placement, surgical revision, ligation of accessory veins).
Primary access patency	Intervention-free access survival defined as the time from fistula or graft creation to any intervention to maintain patency.
Secondary access failure	Permanent failure after the fistula or graft met dialysis suitability criteria with subsequent abandonment.
Noninfectious complications	Stenosis, thrombosis, hand ischemia, aneurysm, pseudoaneurysm, infiltration.
Infectious complications	Fistula or graft cellulitis, abscess, bacteremia.
Access procedures	Angioplasty, stent placement, surgical revision, ligation of accessory veins, superficialization of vein.
Other clinical outcomes	TCVC placement, new AV access surgical creation, AV access-related hospitalization or death.
Limb ischemia following AV access placement	
Symptoms	Paresthesia, pain, hand stiffness, ulceration and tissue loss in the limb with arteriovenous access.

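### Primary patency is defined to end only at an intervention, so an access lost untreated has no event on a literal reading, and patency is overstated where such losses occur

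*Combined protocol and SAP*

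**What the plan says.** Appendix D has one patency row. It defines primary access patency as "Intervention-free access survival defined as the time from fistula or graft creation to any intervention to maintain patency".

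Loss of the access appears in other rows of the same table, none of them tied to patency:

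- Primary access failure is permanent failure before the access is suitable for dialysis. The row adds: "This includes inadequate maturation, thrombosis, failure of first and subsequent cannulations, and other complications leading to nonfunctional fistula or graft".
- Secondary access failure is "Permanent failure after the fistula or graft met dialysis suitability criteria with subsequent abandonment".
- Thrombosis is also listed among the non-infectious complications: "Stenosis, thrombosis, hand ischemia, aneurysm, pseudoaneurysm, infiltration".
- The access procedures are "Angioplasty, stent placement, surgical revision, ligation of accessory veins, superficialization of vein". Abandonment is not a procedure, so it cannot end patency by that route.

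The Vascular access outcomes section only names patency outcomes and cites a reporting standard. The Analytical Plan says that participants who "experience primary or secondary AV access failure will be analyzed as randomized in the intention-to-treat (ITT) analysis", and that "Robust regression and non-parametric methods will be used for comparisons between randomized arms". It gives no event, censoring or competing-risk rule for patency and names no time-to-event method.

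**The concern.** Losing an access without any attempt at salvage is a worse result than keeping it after one angioplasty. Under the operative clause the second access has a patency event and the first does not. An analyst who follows the clause must either censor the lost access or leave it patent to the end of follow-up, and both raise the patency estimate.

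If the arms differ in how often accesses are lost untreated, the between-arm comparison is distorted as well. The arms may well differ in failures overall, since the Background states: "Compared with grafts, fistulas fail more often and necessitate longer times and more subsequent procedures to aid development". The Analytical Plan says that the pilot's results will be considered in designing a larger trial, so a distorted patency estimate could be carried into that design.

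**Working it through.** **The plan's own figure.** The documents give no figure for patency. The one computed design figure is the maximum margin of 0.138 for consent and surgery rates. It reproduces as 1.96 × √(0.25/50) = 0.1386, which is 0.138 when truncated. It does not bear on this point.

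**Inputs.** The plan gives 25 participants per arm and at least 12 months of follow-up. It gives no intervention rate and no untreated-loss rate, so both are assumed and varied:

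- i is the net 12-month risk of intervention: 30%, 40% or 50%.
- a is the net 12-month risk of loss with no prior intervention: 10%, 20% or 30%.

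**Model.** Constant, independent hazards over 12 months, hI = −ln(1 − i) and hU = −ln(1 − a).

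- Loss counted as an event: exp(−(hI + hU)) = (1 − i)(1 − a).
- Literal rule, losses censored: exp(−hI) = 1 − i.
- Literal rule, losses carried event-free: 1 − [hI/(hI + hU)] × [1 − (1 − i)(1 − a)].

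**Worked case, i = 0.40 and a = 0.30.** hI = 0.511 and hU = 0.357. Loss counted: 0.60 × 0.70 = 0.42. Censored: 0.60. Carried: 1 − (0.511/0.868) × 0.58 = 0.658.

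| i | a | Loss counted | Censored | Carried |
|---|---|---|---|---|
| 0.30 | 0.10 | 0.630 | 0.700 | 0.714 |
| 0.30 | 0.20 | 0.560 | 0.700 | 0.729 |
| 0.30 | 0.30 | 0.490 | 0.700 | 0.745 |
| 0.40 | 0.10 | 0.540 | 0.600 | 0.619 |
| 0.40 | 0.20 | 0.480 | 0.600 | 0.638 |
| 0.40 | 0.30 | 0.420 | 0.600 | 0.658 |
| 0.50 | 0.10 | 0.450 | 0.500 | 0.523 |
| 0.50 | 0.20 | 0.400 | 0.500 | 0.546 |
| 0.50 | 0.30 | 0.350 | 0.500 | 0.571 |

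The overstatement runs from 0.050 (i = 0.50, a = 0.10, censored) to 0.255 (i = 0.30, a = 0.30, carried).

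**Between arms.** The effect depends on both rates in each arm:

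- *Same i = 0.40, a = 0.10 against 0.30.* Counting loss, 0.54 against 0.42, a 12-point difference. Censored, 0.60 against 0.60, so it is hidden. Carried, 0.619 against 0.658, so it is reversed by about 4 points.
- *i = 0.40, a = 0.10 against i = 0.50, a = 0.30.* Counting loss, 0.54 against 0.35, or 19 points. Censored, 0.60 against 0.50, or 10 points. Carried, 0.619 against 0.571, or about 5 points. The difference shrinks but keeps its sign.
- *Both arms at 0.50 counting loss, with 10% against 40% of the endings being untreated losses.* Censored, 0.5^0.9 = 0.536 against 0.5^0.6 = 0.660. Carried, 1 − 0.9 × 0.5 = 0.55 against 1 − 0.6 × 0.5 = 0.70. A difference of 12 to 15 points appears where none exists, in favour of the arm with more untreated losses.

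**The case against.** The best defence is the label itself. A permanently clotted or abandoned access has not survived in any ordinary sense, and the table says that it follows published reporting standards. Those standards may supply the missing end event, but they cannot be checked from the documents. This stands in part: the label and the operative clause disagree, and the investigators may have meant loss to count. The written rule still does not say so, and the choice would otherwise be made during analysis.

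Three stronger readings are tempting, and the documents do not support them:

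- *The rule favours fistulas.* The Background expects more fistula failures overall, but the distortion depends on losses with no prior intervention. No split of treated and untreated losses is given. The same sentence expects more procedures with fistulas, and an access treated before it is lost already has its event.
- *A real difference would be reported as none.* That needs equal intervention risk in both arms and censoring of losses. With unequal risks, the second comparison above shows attenuation instead.
- *The rule yields one fixed wrong figure.* The plan does not say whether losses are censored or carried, and the two give different results.

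The consequences are also limited. The Sample Size section makes feasibility the principal aim, and the stated targets are consent and surgery within 90 days. Patency is not among the arm comparisons that the Analytical Plan names; only its general sentence on methods could cover it. Primary and secondary access failure are separate outcomes, so untreated losses remain visible elsewhere. All of this lowers the importance of the point, but does not correct the patency estimate.

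**Conclusion.** The point holds as a defect in one definition. Taken literally, primary patency exceeds intervention-and-loss-free patency whenever some accesses are lost with no prior intervention, and the excess grows with that loss. Under the assumed rates it is 0.05 to about 0.26 at 12 months. A between-arm difference can be attenuated, hidden, reversed or created, depending on each arm's rates. The fact of overstatement follows from the wording; its size rests on assumed rates, constant hazards and independence of intervention and loss. Its direction between arms cannot be determined from the documents.

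The impact is modest. With 25 per arm, the 95% margin for a proportion near 0.5 is 1.96 × √(0.25/25) = 0.196, so sampling error is of the same order as the distortion. The definition should be corrected, but the pilot's feasibility aims do not depend on it.

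**What to change.** Replace the Appendix D definition with: time from creation of the access to the first of (a) any intervention to maintain or restore patency, (b) access thrombosis, or (c) permanent failure or abandonment of the access, applied identically in both arms.

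State at the same time:

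- whether procedures that assist maturation end primary patency. The example procedures in the assisted-maturation row overlap with the general procedure list, and the table does not say;
- how death, transplant and dropout with a patent access are handled, as censoring or as competing events;
- which time-to-event method will be used for patency.

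The cost is a line in Appendix D and a sentence or two in the Analytical Plan. Procedures, thrombosis and access failure are already monitored, so no new outcome and no change in sample size is needed, provided that each event is dated. Reported patency will be lower wherever untreated losses occur.

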Appendix E. Protocol Violation, Expected Events, Cause of Death

A. Protocol violations	
Dropouts and their causes (e.g., withdrawal of consent, transfer to another center, refusal to undergo study-specific assessments)	
B. Expected procedure-related events	
Local events	Systemic events
Bleeding from access site requiring intervention	Allergic reaction to local anesthetic
Nerve injury	Allergic reaction to generalized anesthetic
Ischemia (to nerves or distal extremity)	Heart failure (high output congestive heart failure)
Arterial steal syndrome requiring intervention	Myocardial infarct
Seroma	Pulmonary embolism
	Aspiration pneumonia
	Nosocomial infection
	Sudden death
C. Classification of causes of death	
1. Cardiovascular	
Acute coronary syndromes and related complications	
Heart failure	
Cardiac dysrhythmias	
Valvular disorders	
Myocardial disorders	
Pericardial disorders	
Complications of cardiac or vascular surgery	
Complications of cardiac or vascular procedures	
Cardiac perforation following hemodialysis catheter insertion	
Cardiac arrest during placement of a dialysis catheter in radiology suite	
Acute stroke syndromes and complications (ischemic and hemorrhagic)	
Complications of peripheral vascular disease (examples: ischemic gut, ischemia of the extremities)	
Complications of aortic dissection and aortic aneurysm	
Complications of congenital heart disease	
2. Sudden death at home	
without antecedent illness or procedure that could have contributed to the death.	
3. Infectious	
Bacteremia/sepsis from any source, including complications of vascular access.	
Examples of sources of sepsis: pneumonia, urinary tract, infective endocarditis, intra-abdominal abscess, colitis, septic joint, soft tissue ulcer, dialysis vascular access related bacteremia, dialysis vascular access related sepsis and infective endocarditis, dialysis vascular access related sepsis and osteomyelitis, dialysis vascular access related sepsis and ectopic abscess, infective endocarditis of mechanical valve from infectious complication of dialysis vascular access, etc.	
4. Malignancy-related	
Complications of any malignancy leading to death. This includes metastatic disease leading to withdrawal of care or palliation.	
5. Elective withdrawal from dialysis	
Elective discontinuation of dialysis therapy, in the absence of an acute, antecedent precipitant such as	

an acute medical illness.

6. Other:

